### 5.1.1.1.3 Definition of Maximum Tolerated Dose

The MTD estimate is the highest dose tested of avelumab associated with the occurrence of DLTs within the first 2 cycles of treatment in < 33% of subjects, provided that a higher dose level of avelumab was tested and had an associated DLT rate  $\geq$  33%. If the DLT rate within the first 2 cycles of treatment is < 33% for all tested dose levels, then the MTD will not have been reached.

### 5.1.1.1.4 Definition of Recommended Phase II Dose

The RP2D is defined as the dose of avelumab chosen for further clinical development in pediatrics. Pharmacokinetics, pharmacodynamics, safety, and antitumor activity data can result in selection of an RP2D level that is lower or higher than the current adult dosage of 10 mg/kg, as long as it does not exceed the MTD.

### 5.1.1.1.5 Age Range for Each Cohort in Phase I

The study is aimed at defining a single RP2D in the age group of 0 to < 18 years at the time of first treatment dose. However, if at any time during the study, data suggest a difference in tolerability by age, this will be discussed with the SMC. The following rules will be used:

- The initial cohort will be open to subjects 0 to < 18 years of age; the first 3 subjects will be  $\geq$  1 year of age.
- Subsequent cohorts of 3 to 6 subjects each may be open to subjects 0 to < 18 years of age or a narrower age range, based on emerging data, as agreed on by the SMC.

### 5.1.1.1.6 End of Phase I

When at least 12 DLT-evaluable subjects have been treated at a dose level confirmed to be safe, enrollment in Phase I will be complete and Phase II will begin.

### 5.1.1.2 Phase II Study Design

The determination of the RP2D in children will trigger the enrollment of 2 expansion cohorts. Specific tumors will be chosen for the expansion cohorts based on available data from the Phase I part of the study, ongoing studies with avelumab and other ICIs, clinical and nonclinical combination chemotherapy data, and any published literature. These data may include clinical data with avelumab or with other immune checkpoint inhibitors, or preclinical data providing additional rationale for a specific tumor type.

Each expansion cohort will follow Simon's Optimal Two-stage Design (Simon 1989). If there are 2 or more subjects with confirmed objective response among the first 23 subjects treated at the RP2D, then an additional 33 subjects will be enrolled and treated at that dose level. If there is 1 or no subjects with a confirmed objective response among the first 23 subjects treated at the RP2D with a minimum follow-up of 16 weeks, then the cohort will be closed for further enrollment.

Subjects will return to the clinic at regular intervals for assessments (see Section 7.1 and Table 1).

Avelumab treatment will continue until:

- Confirmed PD (see Section 5.5.1) or death
- Unacceptable toxicity
- Any criterion for withdrawal from the trial or trial treatment is fulfilled (see Section 5.5).

Treatment can continue past the initial determination of confirmed disease progression (see Section 6.2).

Subjects who have experienced a complete response (CR) should be treated for a minimum of 12 months based on clinical judgment of benefit and/or until confirmed progression per irRECIST, unacceptable toxicity, or any criterion for withdrawal occurs, after confirmation of response as specified in this protocol. In case a subject with a confirmed CR relapses after stopping treatment, during long-term follow-up but prior to the End of Trial, 1 re-initiation of treatment will be allowed at the discretion of the Investigator and agreement of the Medical Monitor. In order to be eligible for retreatment, the subject must not have experienced any toxicity that led to treatment discontinuation of the initial avelumab therapy. Prior to re-initiation of the study treatment, malignant disease will be radiologically re-staged to assess all known sites of the disease and to establish a new baseline for subsequent tumor measurements. Relevant safety laboratory results must be available and verified prior to re-initiating treatment. Subjects who re-initiate treatment will stay on study and will be treated and monitored according to the protocol and the Schedule of Assessments (Table 1).

Each subject will be followed for additional 12 months after end of treatment.

The primary Phase II endpoint is confirmed best overall response (BOR) according to RECIST 1.1.

Safety endpoints include incidence of AEs and laboratory abnormalities assessed throughout the trial and evaluated using NCI-CTCAE v4.03, and vital signs.

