Once the RP2D is determined, Phase II will begin with 2 expansion cohorts in 2 specified tumor types. The specified tumor types will be selected based on emerging data from this study and other ongoing studies. These data may include clinical data with avelumab or with other immune checkpoint inhibitors, or preclinical data providing additional rationale for a specific tumor type. Each expansion cohort will follow Simon's Optimal Two-stage Design. If there are 2 or more subjects with confirmed objective responses within the first 23 subjects treated at the RP2D, then an additional 33 subjects will be enrolled and treated at that dose level. If there are 1 or no subjects with confirmed objective responses in the first 23 subjects treated at the RP2D within a minimum follow-up of 16 weeks, then the cohort will be closed for further enrollment.

The study is aimed at defining a single RP2D in the age group 0 to < 18 years. However, if at any time during the study, data suggest a difference in tolerability by age, this will be discussed with the Safety Monitoring Committee (SMC). The following rules will be used:

- The first 3 subjects in the initial cohort will be 1 to < 18 years of age.
- Subsequent cohorts may be open to subjects 0 to < 18 years of age, or a narrower age range, based on emerging data, as agreed by the SMC.

Avelumab will be administered every 2 weeks until confirmed progression, death, unacceptable toxicity, or any criterion for withdrawal occurs. A cycle is defined as 2 weeks. In Phase I, the DLT observation period is defined as a 28-day period (2 cycles) beginning with the first avelumab administration. Each subject will be followed for 12 months after his/her end of treatment.

Baseline imaging will be performed within 28 days prior to registration and Cycle 1 Day 1 treatment in order to establish Baseline disease status of target and nontarget lesions according to RECIST 1.1. Acceptable modalities include CT scans (neck, chest, abdomen, and pelvis as

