Tumor evaluation (see Section 7.3) will be performed every 8 weeks starting at Cycle 5 for the first 24 weeks, then every 12 weeks until the end of treatment or withdrawal from the study, and at the End of Treatment/Withdrawal Visit if more than 4 weeks has passed since the last evaluation.

Subjects will receive avelumab by iv infusion following pretreatment with an antihistamine (H1 receptor blocker such as diphenhydramine) and acetaminophen (paracetamol; oral or iv), approximately 30 to 60 minutes prior to each dose, once every 2 weeks for the first 4 infusions (see Section 5.1.2).

Assessments to be performed during the treatment period are presented in [Table 1](#) and [Table 2](#).

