### 7.3 Efficacy Assessments

To determine the ORR, the anticancer activity of avelumab will be evaluated by performing CT/MRI scans until confirmed disease progression or the start of new anticancer therapy.

A CT or MRI will be performed every 8 weeks for the first 24 weeks, then every 12 weeks thereafter (a window of 5 days prior to dosing is allowed, and  $\pm 5$  days at the End of Treatment Visit). In case partial response (PR), complete response (CR), or progressive disease (PD) is observed according to RECIST 1.1, a confirmation CT or MRI should be performed according to RECIST 1.1, preferably at the regularly scheduled 8-week assessment interval, but no sooner than 4 weeks after the initial documentation of response or confirmed disease progression. Tumor assessment should be repeated at the End of Treatment Visit if more than 4 weeks have passed since the last evaluation.

Treatment decisions will be made by the Investigator based on the Investigator's assessment of disease status. Investigator's assessment of objective tumor response to treatment will be performed according to RECIST 1.1 (all measurements should be recorded in metric notation, as described in RECIST 1.1).

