2.0	22 June 2021	PPD	
Background: the avelumab EMA PIP has been modified and evaluation of avelumab monotherapy in pediatric patient has been terminated after Phase I of this study. Therefore, analysis of Phase II data will not be completed. The analyses described have been modified according to the needs of the Phase I reporting. All changes implemented in the IAP are listed below:
 
 • Section 6: Update trigger for Final Analysis to occur after all subjects have withdrawn from the trial, rather than 1 year after last End of Treatment visit • Section 7: Update to drop inclusion of analysis of gestational age and weight at birth; remove text indicating efficacy analysis will not be performed for Phase I • Section 8.2: Add specifics regarding tumor category subgroup analysis; specify all efficacy analyses will be performed overall and by tumor category • Section 9: Update text for last-alive date to match current IAP language • Section 10.1: Update disposition table to count subjects treated, rather than subjects enrolled; update disposition table to remove study "completion" category, include death and progressive disease as reason for study discontinuation; remove table of subjects by region and site • Section 10.2.2: Added section to specify COVID-19 protocol deviation listing • Section 11.1: Removal of gestational age, pooled geographic region, birth weight from demographics table • Section 11.2: Update to specify medical history details will be listed only. • Section 11.3: Update to remove site of primary tumor and add tumor category to disease history table • Section 11.4: Update to include all prior anti-cancer treatments on a single listing, rather than have three separate listings • Section 12: Update to remove prior medications table; include prior medications in concomitant medication listing • Section 13: Sections for and analyses of partial doses, infusion rate reductions, and infusion interruptions removed • Section 14.1: Added details regarding analysis of objective response; updated listings to include tumor assessment and reason for overall response of NE to a single listing, rather than separate listings • Section 14.2 and 14.3: Update to clarify that the analyses will not be conducted if no responders are observed • Section 14.4: Update to analyze PFS in weeks, not months; update to provide details on PFS analysis (add Kaplan meier estimates)

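### The stage-1 closing rule in Phase II allows a count from 16 weeks of follow-up, when a response first seen on the week-16 scan cannot yet be confirmed

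*Protocol*

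**What the plan says.** Protocol 5.1.1.2 applies Simon's optimal two-stage design to each expansion cohort.

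- **Continue:** the condition is "If there are 2 or more subjects with confirmed objective response among the first 23 subjects treated at the RP2D". In that case stage 2 recruits 33 more at the same dose.
- **Close:** the condition is 1 or no confirmed response in the same 23, "with a minimum follow-up of 16 weeks". Recruitment to that cohort then ends.

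The synopsis (Methodology) gives the same rule but writes "within a minimum follow-up of 16 weeks". In both places the 16 weeks is attached only to the closing limb.

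The imaging schedule is in two sections. Protocol 7.1.2 sets tumor evaluation "every 8 weeks starting at Cycle 5 for the first 24 weeks". Protocol 7.3 asks for a confirmatory scan, preferably at the next 8-week assessment, but "no sooner than 4 weeks after the initial documentation of response or confirmed disease progression". Protocol 8.5.2.3 requires confirmation of both CR and PR before either counts as an objective response.

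No readable text says what happens to a PR or CR that is still unconfirmed when the 23 subjects are counted. The sample-size section is redacted. The Modification History of SAP v2.0 (SAP Section 3) records that monotherapy evaluation stopped after Phase I and that "analysis of Phase II data will not be completed".

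**The concern.** A two-stage design of this kind takes each stage-1 subject's response status as settled when the count is made. Here the earliest permitted count is at the nominal time of the second on-treatment scan. That scan can confirm a response first seen at week 8, but a response it shows for the first time cannot yet be confirmed. A subject with such a response does not count towards the 2 needed to continue.

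The cohorts at risk are borderline ones, with 0 or 1 confirmed response and enough pending ones to reach 2. Stopping enrollment in such a cohort could end the evaluation of an active tumor type shortly before the deciding scan.

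**Working it through.** **Timing, from the protocol alone**

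- First on-treatment scan: Cycle 5, Day 57 (Table 1), nominal week 8.
- Second scan: Day 57 + 56 = Day 113, nominal week 16. Third: week 24.
- Earliest confirmation of a response first seen at week 16: Day 113 + 28 = Day 141, week 20. On the preferred 8-week schedule: week 24.
- If the week-16 scan is taken 5 days early, as the Table 1 footnote on tumor assessments allows: (112 − 5 + 28)/7 = 19.3 weeks, still after week 16.
- A response first seen at week 8 can be confirmed from week 12, or on the week-16 scan, so it is safe.

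**The plan's own figures**

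23 + 33 = 56 per cohort; 2 × 23 = 46 and 2 × 56 = 112, which match the planned Phase II numbers. The error rates and hypotheses are not readable, so the design cannot be reproduced from the documents' inputs. In an exact search for the optimal design over ten assumed input sets, only a null rate of 5%, an alternative of 15%, one-sided alpha 0.05 and power 0.80 gave 1/23 and 56. Under those inputs the final rule is to reject the null with 6 or more responses of 56 (cut-off 5/56), with exact alpha 0.04996 and power 0.8003. These inputs are **assumptions** for everything below.

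**Model for the loss**

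Let f be the share of eventual confirmed responses first seen at week 16 or later (assumed: one fifth or one third). Let the 23 enroll evenly over E weeks, with the count made when the last one reaches 16 weeks. Follow-up then runs from 16 to 16 + E weeks. The share of subjects too early to confirm a week-16 response is s = 4/E (20-week threshold) or 8/E (24-week threshold). A response is counted at stage 1 with probability q = 1 − f·s.

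- P(pass stage 1) = P(Bin(23, 0.15q) ≥ 2)
- Power = Σₓ P(X = x) · P(Bin(x, q) ≥ 2) · P(Bin(33, 0.15) ≥ 6 − x), with X ~ Bin(23, 0.15)

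**Baseline, all responses counted.** P(close) = 0.85²³ + 23 × 0.15 × 0.85²² = 0.0238 + 0.0966 = 0.120. So P(pass) = 0.880, and power is 0.800.

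**Staggered enrollment**

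| f | E (weeks) | Threshold (weeks) | s | q | P(pass) | Power |
|---|---|---|---|---|---|---|
| 1/3 | 26 | 24 | 0.308 | 0.897 | 0.835 | 0.766 |
| 1/3 | 26 | 20 | 0.154 | 0.949 | 0.859 | 0.785 |
| 1/3 | 52 | 24 | 0.154 | 0.949 | 0.859 | 0.785 |
| 1/3 | 52 | 20 | 0.077 | 0.974 | 0.870 | 0.793 |
| 1/5 | 26 | 24 | 0.308 | 0.938 | 0.855 | 0.781 |
| 1/5 | 26 | 20 | 0.154 | 0.969 | 0.868 | 0.791 |
| 1/5 | 52 | 24 | 0.154 | 0.969 | 0.868 | 0.791 |
| 1/5 | 52 | 20 | 0.077 | 0.985 | 0.874 | 0.796 |

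**Extreme case.** All 23 at exactly 16 weeks (s = 1): P(pass) 0.685 and power 0.639 at f = 1/3; 0.781 and 0.722 at f = 1/5.

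**Type I error.** With a true rate of 0.05 it is 0.050 when all responses count. It falls to 0.042 in the extreme case with f = 1/5.

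**The case against.** The best counter-argument is that 16 weeks is a floor. Section 5.1.1.2 fixes the earliest closure, not a look at week 16 for each subject. The sponsor may wait for a pending scan, and subjects enrolled earlier have longer follow-up anyway. This stands. It confines the problem to the last-enrolled subjects and to a count made at the first permitted moment. It does not remove it, because nothing readable requires the wait.

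A reader might infer that the rule makes every week-16 responder a non-responder, and so that power drops to about 0.64. The documents do not support that. The figure needs all 23 subjects to start together and one third of responses to be late. The synopsis wording could be taken as a 16-week cut-off for everyone, but it is paired with the word minimum and differs from the body text. That is a reason to align the two passages, not evidence that a cut-off was intended.

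Three further objections also stand. The hypotheses, final cut-off, late-response share and enrollment period are assumptions, and a rule for pending responses may sit in the redacted section. The modeled loss includes responses first seen after week 16, which the fix below would not recover, so its gain is smaller than the loss shown. And Phase II analysis was dropped, so no analysis planned in SAP v2.0 depends on the rule.

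**Conclusion.** The timing conflict is real and follows from the protocol's own schedule: closure on confirmed responses is allowed from week 16, but a response first seen at week 16 is confirmable only from about week 20, or week 24 on the preferred schedule. As written, the rule permits a cohort to be closed with a decisive response pending.

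The size is modest. Under the assumptions stated, staggered enrollment over 26 to 52 weeks costs between about 0.4 and 3.4 percentage points of power (0.800 to between 0.796 and 0.766). The error runs one way: it adds false closures and does not raise type I error. It would be wrong to infer that any Phase I result is affected. The point is confined to the Phase II rule in protocol version 2.0 and any reuse of it. It is a minor point and a cheap improvement.

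**What to change.** Give the synopsis and Section 5.1.1.2 the same wording, and state two things:

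1. The stage-1 count is made when each of the 23 subjects has a final confirmed or not-confirmed status for any response first seen by week 16. That status is reached through progression, leaving the study, or the confirmatory scan at week 20 to 24.
2. The cohort is not closed while a pending PR or CR could change the decision.

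The cost is a text change in two places and a delay of up to 8 weeks before closure, only when a pending response matters. The Phase I analysis and report need no change.

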### 5.1.2 Trial Treatment Administration and Schedule

The trial Schedule of Assessments is presented in Table 1, and the Schedule of Assessments - PK and Antidrug Antibody (ADA) Sampling in Table 2.

Subjects will receive iv infusions of avelumab once every 2 weeks.

To mitigate infusion-related reactions, premedication with antihistamine (H1 receptor blocker such as diphenhydramine) and acetaminophen (paracetamol), based on local treatment standards and guidelines, approximately 30 to 60 minutes prior to each dose, once every 2 weeks for the first 4 doses of avelumab is mandatory. Premedication can be administered beyond the fourth dose of avelumab based upon clinical judgment and presence/severity of prior infusion reactions. This regimen may be modified based on local treatment standards and guidelines as appropriate, provided it does not include systemic corticosteroids (steroid premedication specifically for avelumab is not permitted).

The formulation and packaging information of avelumab is provided in Section 6.

### 5.1.2.1 Standard of Care

Not applicable.

### 5.1.3 Dose Modification and Adverse Drug Reactions Requiring Treatment Discontinuation

#### 5.1.3.1 Dose Modification for Avelumab

The dose of avelumab will be calculated based on the weight of the subject determined within 72 hours prior to the day of drug administration. The dose of avelumab used for the previous administration can be repeated if the change in the subject's weight is within 10% of the weight used for the last dose calculation.

In Phase I, dose escalation/de-escalation rules will follow the mTPI method (see Section 5.1.1.1.1). In Phase II, each subject will stay on the avelumab RP2D dose unless treatment needs to be stopped. There will be no dose reductions in Phase II. Dosing modifications (changes in infusion rate) are described in Section 5.1.3.2 and Section 6.5.5.

#### 5.1.3.2 Adverse Drug Reactions Requiring Avelumab Treatment Discontinuation or Modifications

The following adverse drug reactions (ADRs; for definition, see Section 7.4.1.1) require permanent treatment discontinuation of avelumab:

- Any Grade 4 ADR, except for the following:
  - Grade 4 lipase or amylase abnormality that is not associated with clinical manifestations of pancreatitis. The Medical Monitor must be consulted for such lipase and amylase abnormalities.
  - Grade 4 neutropenia of  $\leq 7$  days in duration
  - Grade 4 thrombocytopenia without bleeding
  - Other single laboratory values out of normal range that do not have any clinical correlate and resolve to baseline within 7 days with adequate medical management.
- Any Grade 3 ADR except for any of the following:
  - Transient ( $\leq 72$  hours) Grade 3 flu-like symptoms or fever, which are controlled with medical management
  - Transient ( $\leq 72$  hours) Grade 3 fatigue, local reactions, headache, nausea, or emesis that resolve to Grade  $\leq 1$  or baseline with appropriate medical management
  - Grade 3 diarrhea or Grade 3 skin toxicity that resolves to Grade  $\leq 1$  in less than 7 days after medical management (eg, immunosuppressant treatment) has been initiated
  - Grade 3 lipase or amylase abnormality that is not associated with clinical manifestations of pancreatitis. The Medical Monitor must be consulted for such lipase and amylase abnormalities.

- Other single laboratory values out of normal range that do not have any clinical correlate
- Tumor flare phenomenon defined as local pain, irritation, or rash localized at sites of known or suspected tumor
- Any Grade 2 ADR should be managed as follows:
  - Infusion should not be given in case of ongoing Grade 2 ADR on the day of trial treatment administration.
  - Treatment can be resumed according to original schedule once ADR resolves to Grade  $\leq 1$ . Up to 2 subsequent study drug doses may be omitted. If more than 2 doses are skipped, treatment may be resumed after consultation with the study Medical Monitor.

See the guidelines for handling infusion-related reactions (Section 6.5.5.1), severe hypersensitivity reactions and flu-like symptoms (Section 6.5.5.2), and irAEs (Section 6.5.5.3).

